9 QUALITY CONTROL AND ASSURANCE

Training will occur at an investigator meeting or at the site initiation visit or both, and instruction manuals (eg, laboratory manuals and pharmacy manuals) will be provided to aid consistency in data collection and reporting across sites.

Clinical sites will be monitored by Shire HGT or its designee to ensure the accuracy of data against source documents. The required data will be captured in a validated clinical data management system that is compliant with the Food and Drug Administration (FDA) 21 Code of Federal Regulations (CFR) Part 11 Guidance. The clinical trial database will include an audit trail to document any evidence of data processing or activity on each data field by each user. Users will be trained and given restricted access, based on their role in the study, through a password protected environment.

Data entered in the system will be reviewed manually for validity and completeness against the source documents by a clinical monitor from Shire HGT or its designee. If necessary, the study site will be contacted for corrections or clarifications; all missing data will be accounted for.

SAE information captured in the clinical trial database will be reconciled with the information captured in the Pharmacovigilance database.

10 PLANNED STATISTICAL METHODS

10.1 General Statistical Methodology

This is an open-label extension of study HGT-SAN-055 to evaluate the long-term safety and clinical outcomes of intrathecal administration of rhHNS in patients with Sanfilippo syndrome type A (MPS IIIA). The statistical methodology supporting the trial will focus on descriptive rather than inferential approaches, given the early phase and objectives of this trial.

Data will be summarized by dose group (10 mg per month, 45 mg per month and 45 mg every other week) with respect to demographic and baseline characteristics, efficacy variables and safety variables. Summary statistics for continuous variables will include the n, mean, standard deviation, median, minimum and maximum. Categorical variables will be summarized in a contingency table by the frequency and percentage of patients in each category. Data will be plotted to assess trends across time.

All hypothesis tests will be 2-sided and will be performed at the 0.05 level. Hypothesis testing will be viewed as exploratory. Any resulting p-values will not be regarded as a firm support for conclusions, but rather suggestive of areas of examination in future studies. In general, variables will be quantified as a change from the baseline value. The null hypothesis will be that there is no difference in the change from baseline between dose groups. Note that the baseline visit for this study will be the first day the patient received his/her IT dose of rhHNS in study HGT-SAN-055.

The primary objective of this trial is to assess the long term safety of rhHNS administration via a surgically implanted intrathecal drug delivery device (IDDD). Hence an extensive safety assessment will be performed. The safety analyses will consist of all enrolled patients. To evaluate safety, adverse experiences will be tabulated by dose group. Vital signs, electrocardiograms, serum and CSF components and chemistries, hematology, and urinalysis safety monitoring will be listed for each patient and abnormal values will be flagged. In addition, anti-rhHNS antibodies (in CSF and serum) will also be listed. No formal statistical tests will be performed on the safety parameters.

10.2 Determination of Sample Size

Since this is an extension study, sample size is determined by the number of patients who completed HGT-SAN-055 (maximum of 12 patients) and enrolled in this study

10.3 Analysis Populations

The analysis population consists of all eligible patients from HGT-SAN-055 who have agreed to participate in the extension study. Both safety and efficacy analyses would be performed using the above mentioned population.

10.4 Demographics and Baseline Characteristics

Patient disposition for those enrolled will be presented in a summary table using number and percentage of patients enrolled, completed or discontinued/withdrew, by dose group. The reasons for discontinuation/withdrawal will also be presented.

Demographic and baseline characteristics (eg, age, race, ethnicity, medical history, and surgical history) will be reported in summary tables.

10.5 Statistical Analysis of Pharmacokinetic Variables

Not applicable

10.6 Efficacy, Safety, and Pharmacodynamic Evaluations

10.6.1 Primary Analyses

10.6.1.1 Safety Analysis

In general, safety assessments will be based on all assessments post-baseline. The assessment of safety will be based primarily on the frequency of treatment-emergent adverse events, due to study drug and on the frequency of clinically notable abnormal vital sign and laboratory values. Changes from baseline will be calculated by subtracting the baseline value from the post-baseline value.

All enrolled patients will be included in the safety analysis. Patients will be grouped according to the actual dose received.

No formal statistical test will be performed in the safety evaluations. Vital sign measurements, clinical chemistry, and hematology safety monitoring will be listed for each patient, and abnormal values will be flagged. These will also be summarized at each time point, including change from baseline.

Adverse events will be recorded throughout the study and at early termination. Adverse events and medical conditions will be coded using the Medical Dictionary for Regulatory Activities (MedDRA) Version 9.0 or later. In all cases (with the exception of device-related events), adverse event summaries will be based on all adverse event recorded beginning on Study Day 1 (treatment-emergent AEs).

Adverse events will be summarized by presenting, for each treatment group, the number and percentage of patients having any adverse event, having an adverse event in system organ class, and having each individual adverse event. Note that in any given category (eg, system organ class) a patient will only be counted once. In addition, those events which resulted in death or were otherwise classified as serious will be presented in a separate listing. The incidence of treatment-emergent adverse events (new or worsened from baseline) will be summarized by system organ class, severity, type of adverse event and relationship to trial medication.

Adverse events that occur up to 30 days after the last dose of study drug will be considered “on-treatment”. Adverse events which are deemed probably or possibly related to the device will be summarized by dose group and overall.

Laboratory data will be listed by patient and dose group. Patients with newly occurring abnormalities outside the normal range will be flagged and listed separately and summarized. Mean change from baseline values or shift tables will also be provided by dose group at each visit.

Vital signs data will be listed by patient and dose group. Furthermore, mean changes from baseline for vital sign data will be summarized for each dose group. Shift tables may be presented, utilizing reference ranges. Patients with notably abnormal values will be identified and listed separately along with their values.

ECG assessments will be listed by patient and dose group. Mean changes from baseline for ECG data will be summarized for each dose group. Patients with any clinically significant findings and/or conduction abnormalities will be listed separately along with their values.

For those patients who fail to complete the study, the reason for discontinuation will be listed by patient and dose group.

Listings of all study safety data will be presented.

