5.2 Inclusion Criteria

Each patient must meet the following criteria to be considered eligible for enrollment in this study.

1. Patients must have completed all study requirements and assessments for Study HGT-SAN-055 prior to enrolling in this extension study and must have no safety or medical issues that contraindicate participation.
2. The patient, patient's parent(s), or legally authorized guardian(s) must have voluntarily signed an Institutional Review Board / Independent Ethics Committee-approved informed consent form after all relevant aspects of the study have been explained and discussed with the patient. The guardians' consent and patient's assent, as relevant, must be obtained.
3. The patient has received and tolerated treatment with rhHNS, completed the End of Study visit, and has received at least 80% of the total planned infusions within the last 6 months in study HGT-SAN-055 (ie, at least 5/6 ([Group 1 or 2] or 10/12 infusions [Group 3])).
4. Patients must be medically stable, in the opinion of the Investigator, to accommodate the protocol requirements, including travel, assessments, and IDDD surgery (if necessary for replacement purposes), without placing an undue burden on the patient/patient's family.

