5.3 Exclusion Criteria

Subjects will be excluded from the study if there is evidence of any of the following criteria at screening or at anytime during the study:

1. The patient has experienced an adverse reaction to study drug in Study HGT-SAN-055 that contraindicates further treatment with rhHNS.
2. The patient has a known hypersensitivity to the active ingredient or any excipients in rhHNS drug product.
3. The patient has significant non-MPS IIIA related central nervous system (CNS) impairment or behavioral disturbances that would confound the scientific integrity or interpretation of study assessments, as determined by the Investigator.
4. The patient has significant MPS IIIA behavioral-related issues, as determined by the Investigator, which would preclude performance of study neurocognitive and developmental testing procedures.
5. The patient is pregnant, breast feeding, or is a female patient of childbearing potential who will not or cannot comply with the use of an acceptable method of birth control, such as condoms, barrier method, oral contraception, etc.
6. The patient has any known or suspected hypersensitivity to anesthesia or is thought to have an unacceptably high risk for anesthesia due to airway compromise or other conditions.

7. The patient has a history of poorly controlled seizure disorder.
8. The patient is currently receiving psychotropic or other medications, which in the Investigator's opinion, would be likely to substantially confound test results and the dose and regimen of which cannot be kept constant throughout the study.
9. The patient cannot sustain absence from aspirin, non-steroidal medications, or medications that affect blood clotting within 1 week prior to a relevant study-related procedure (eg, device implantation if applicable), or has ingested such medications within 1 week before any procedures in which any change in clotting activity would be deleterious.
10. The patient has received treatment with any investigational drug (other than rhHNS) intended as a treatment for MPS IIIA or used any other intrathecal delivery device other than what was used in Study HGT-SAN-055, within the 30 days prior to, or during the study, or is currently enrolled in another study that involves an investigational drug or device (screening through safety follow-up contact).
11. The patient has received a hematopoietic stem cell or bone marrow transplant.

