8.1 Screening Visit/Baseline Visit

All Screening assessments for this study are to have been performed during the Week 26 (Groups 1 and 2) or Week 28 (Group 3) (30 [\pm 7] days after the last rhHNS administration) EOS procedures in HGT-SAN-055. If less than 60 days have elapsed since completion of the EOS assessments for HGT-SAN-055, the assessments detailed in this Screening visit are not required to be repeated. The Baseline Visit for this study will be the first day the patient received his/her IT dose of rhHNS in Study HGT-SAN-055.

If more than 60 days have elapsed following the HGT-SAN-055 EOS procedures, patients will be evaluated for enrollment in HGT-SAN-067 on a case-by-case basis by the Investigator. A decision about enrollment will be made following discussion with the Medical Monitor. If the patient is enrolled, the following assessments are to be repeated within 30 days prior to the first scheduled intrathecal rhHNS dose:

- Physical examination
- Height and weight
- Head circumference
- ECG
- Vital signs
- Hematology
- Serum chemistry
- Urinalysis
- Neurological examination (performed prior to the administration of anesthesia)
- Neurodevelopmental assessments (performed prior to the administration of anesthesia)
- General anesthesia: administration of anesthesia will be given prior to the following assessments:
 - ABR
 - MRI of the head
- CSF sample collection (chemistry, cell count, heparan sulfate and heparan sulfate derivatives, and other MPS exploratory biomarkers) via the IDDD
- Urine heparan sulfate and heparan sulfate derivatives

- Serum heparan sulfate and heparan sulfate derivatives
- Anti-rhHNS antibody testing
- Children's Sleep Habits Rating Scale
- CHQ-50
- CHQ-87
- ITQOL
- Concomitant medications, therapies, and procedures
- AE assessments

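### Safety percentages counted from the first HGT-SAN-055 dose, but only in children later admitted to the extension, cannot contain treatment-limiting intolerance from the first 6 months

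*Protocol*

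**What the plan says.** Three parts of the protocol bear on this.

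- **Clock.** Section 8.1 sets time zero: "The Baseline Visit for this study will be the first day the patient received his/her IT dose of rhHNS in Study HGT-SAN-055". Section 10.1 repeats it for the analysis. Section 10.6.1.1 then says of safety: "In general, safety assessments will be based on all assessments post-baseline". The same section describes treatment-emergent events as those new or worse relative to baseline, and takes laboratory, vital-sign and ECG changes from that baseline.
- **Population.** Section 10.3 defines one population, used for both safety and efficacy: "The analysis population consists of all eligible patients from HGT-SAN-055 who have agreed to participate in the extension study". Section 10.4 tabulates disposition only for those enrolled.
- **Entry conditions.** Section 5.2, criterion 3, begins "The patient has received and tolerated treatment with rhHNS, completed the End of Study visit" and adds receipt of at least 80% of planned infusions (5 of 6 in Groups 1 and 2, 10 of 12 in Group 3). Section 5.3, criterion 1, excludes a patient if "The patient has experienced an adverse reaction to study drug in Study HGT-SAN-055 that contraindicates further treatment with rhHNS".

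Nothing in section 10 brings in HGT-SAN-055 patients who did not continue, or separates the HGT-SAN-055 period from the extension period.

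**The concern.** Restricting an extension study to those who continued is legitimate, and the primary objective is worded that way. The difficulty is the pairing. The clock starts at the first HGT-SAN-055 dose, but membership is settled about 6 months later by what happened in between. A child whose reaction ended treatment in HGT-SAN-055 is absent from both numerator and denominator, while the continuers' first 6 months lie inside the stated safety window.

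Long-term safety and tolerability is the primary objective, and results are tabulated side by side by dose group. A reader of a table headed as covering the time since first dose would take it to describe what happened to children started on each regimen. For treatment-limiting events it cannot do that.

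**Working it through.** **Inputs from the protocol**

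- Time zero: first HGT-SAN-055 dose (8.1, 10.1).
- Safety window: all post-baseline assessments (10.6.1.1).
- Population: extension enrollees (10.3).
- HGT-SAN-055 treatment: 6 months (Synopsis, Study Design).
- Sample size: at most 12 patients who completed HGT-SAN-055 and enrolled (10.2). This is a cap with no power calculation behind it, so there is no design figure to reproduce.
- The 80% rule is arithmetically consistent: 5/6 = 10/12 = 83.3% pass, while 4/6 = 66.7% and 9/12 = 75% fail.

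**Inputs not in the protocol**

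The numbers of HGT-SAN-055 starters and dropouts are not given. I assume 12 starters, of whom k stop for intolerance before rollover, and m enrollees with a treatment-limiting event later.

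**Step 1: the first 6 months.** An enrollee must have tolerated and completed HGT-SAN-055. The number of treatment-ending intolerance events in that period is therefore 0 among enrollees whatever the true risk. An observed zero there carries no information.

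**Step 2: the cumulative percentage.** From first dose, the planned population gives m/(12 − k). All starters give (k + m)/12.

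| k | m | Planned population | All starters |
|---|---|---|---|
| 0 | 0 | 0/12 = 0% | 0/12 = 0% |
| 1 | 0 | 0/11 = 0% | 1/12 = 8.3% |
| 2 | 0 | 0/10 = 0% | 2/12 = 16.7% |
| 3 | 0 | 0/9 = 0% | 3/12 = 25.0% |
| 0 | 1 | 1/12 = 8.3% | 1/12 = 8.3% |
| 1 | 1 | 1/11 = 9.1% | 2/12 = 16.7% |
| 2 | 1 | 1/10 = 10.0% | 3/12 = 25.0% |
| 3 | 1 | 1/9 = 11.1% | 4/12 = 33.3% |

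For k = 1, m = 0, the upper limit of the exact two-sided 95% interval is 28.5% for 0/11 and 38.5% for 1/12.

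**Step 3: how likely any loss is.** If each of 12 starters has probability p of stopping for intolerance within 6 months, the chance that at least one is removed before rollover is 1 − (1 − p)^12. For assumed p of 5%, 10%, 20% and 30% this is 46%, 72%, 93% and 99%.

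**Step 4: which tables are affected.** For laboratory, vital-sign and ECG changes the clock is explicit. For adverse event counts it follows from the post-baseline rule and the definition of treatment-emergent, but it is not settled. The same section starts the summaries on Study Day 1, which is not defined, and section 7.21.1 starts event monitoring at consent to this study. The three statements do not agree on when counting begins.

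**The case against.** The strongest reply is that HGT-SAN-055 is itself the safety and dose-ranging study, so early intolerance is reported there and the extension need not repeat it. Moreover, 0/11 is what an enrollee-only table starting at the first HGT-SAN-067 dose would show as well, so the gap from 1/12 measures the choice of population, not the clock. Both observations are correct. What they do not remove is the meaning attached to the figure. Counted from extension entry and labelled as conditional on continuing, 0/11 is a fair statement. Counted from first dose, it appears to cover 6 months in which the event was impossible for anyone in the table.

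A second reply is that the adverse event tables may already run on an extension clock, given Study Day 1 and collection from consent. That is possible, but the post-baseline rule says otherwise, so the text needs reconciling either way.

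A third is that section 4.1 expects everyone to continue. It expects this of patients who successfully complete HGT-SAN-055, not of all who started.

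Some stronger readings are tempting but not supported:

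- A reader might infer an immortal person-time bias, with 6 of 48 months (12.5%) diluting event rates. Section 10 plans no person-time or time-to-event analysis. Events are reported as numbers and percentages of patients, and for a fixed set of enrollees a longer window can only keep or raise that percentage.
- A reader might infer that the month 12 to 48 neurocognitive and imaging means are distorted in a way that pooling would repair. Non-continuers have no observations at those visits, so adding them leaves those means unchanged.
- A reader might infer that the first 6 months are free of all intolerance. Tolerated adverse events remain possible, as do 1 of 6 or 2 of 12 missed doses.
- A reader might infer that a particular dose group is flattered. No dropout figure by regimen is given.

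**Conclusion.** The point holds for cumulative from-first-dose adverse event and tolerability percentages, overall and by dose group. They exclude treatment-limiting intolerance in the first 6 months by construction and understate it relative to all patients started on each regimen.

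The size cannot be fixed from the protocol. Under the assumption of 12 starters, one early stop and no later event turns 8.3% into 0%; two early stops and one later event turn 25.0% into 10.0%; with no early stops there is no bias. The 12 in section 10.2 is a ceiling on completers who enrol, so using it as the number of starters is an assumption.

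This is worth correcting because it touches the primary safety tables and is cheap, but it does not undermine the study. The conclusion rests on the original protocol and Amendment 1, which read alike here; the cover lists later amendments that are not shown.

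**What to change.** In sections 10.3 and 10.6.1.1:

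1. Give any cumulative adverse event or treatment-discontinuation summary counted from the first HGT-SAN-055 dose with all patients dosed in HGT-SAN-055 as denominator, by regimen.
2. Present enrollee-only summaries separately for the HGT-SAN-055 period and for the period from the first HGT-SAN-067 dose, labelled as conditional on continuation.
3. Define Study Day 1 and reconcile it with the post-baseline rule in 10.6.1.1 and with event collection from consent in 7.21.1.

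Pre-treatment HGT-SAN-055 values stay as the reference for change from baseline. No new data are needed, since the sponsor holds the HGT-SAN-055 data and already uses them for baseline. The cost is a few sentences of protocol text and one more set of descriptive tables.

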2 STUDY OBJECTIVES

2.1 Primary Objective

The primary objective(s) of this study is:

To collect long-term safety and tolerability data in patients with Sanfilippo Syndrome Type A (MPS IIIA) who received rhHNS via a surgically implanted intrathecal drug delivery device (IDDD) in study HGT-SAN-055 and elected to continue therapy.

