3 STUDY ENDPOINTS

3.1 Primary Endpoint

The primary endpoint of this study is:

To determine the long-term safety of intrathecal rhHNS administration, as measured by adverse events (by type and severity), changes in clinical laboratory testing (serum chemistry including liver function tests, hematology, and urinalysis), electrocardiograms, CSF chemistries (including cell counts and inflammatory markers), and anti-rhHNS antibodies (in CSF and serum).

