Probably Related	A clinical event or laboratory abnormality with a reasonable time sequence to administration of study drug, unlikely to be attributable to concurrent disease or other drugs and chemicals and which follows a clinically reasonable response on de-challenge. The association of the clinical event or laboratory abnormality must also have some biologic plausibility, at least on theoretical grounds.
Definitely related	The event follows a reasonable temporal sequence from administration of the medication, follows a known or suspected response pattern to the medication, is confirmed by improvement upon stopping the medication (dechallenge) and reappears upon repeated exposure (rechallenge).

Table 7-5 Adverse Event Relatedness

Relationship to Product(s)	Definition
	Note that this is not to be construed as requiring re-exposure of the patient to study drug; however, the determination of definitely related can only be used when recurrence of event is observed.

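### Section 10.6.1.1 makes drug-attributed adverse events the primary basis for judging safety, contradicting the all-causality primary endpoint and the section's own tables

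*Protocol*

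**What the plan says.** Under Primary Analyses, Section 10.6.1.1 opens with what the safety conclusion rests on: "The assessment of safety will be based primarily on the frequency of treatment-emergent adverse events, due to study drug". The same sentence adds a second component, clinically notable vital-sign and laboratory abnormalities, which carries no attribution condition. The wording is identical in the original protocol of 21 June 2010 and in Amendment 1.

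The primary endpoint in Section 3.1 is broader: "To determine the long-term safety of intrathecal rhHNS administration, as measured by adverse events (by type and severity", together with laboratory, ECG, CSF and antibody data. Section 10.1 gives the primary objective as to "assess the long term safety of rhHNS administration via a surgically implanted intrathecal drug delivery device (IDDD", and sets a general rule without a causality condition: "To evaluate safety, adverse experiences will be tabulated by dose group".

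Later in Section 10.6.1.1, the planned tables give "the number and percentage of patients having any adverse event, having an adverse event in system organ class, and having each individual adverse event". Relationship to trial medication appears there as one breakdown among several. Deaths and other serious events go into a separate listing, device-related events get their own summary, and the section ends by promising listings of all safety data.

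**The concern.** The sentence that names the primary basis for judging safety counts a narrower set of events than the primary endpoint does. An event enters that basis only if it is put down to the drug. Section 7.21.2.2 leaves that decision to the investigator. The trial has no control (Section 6.1.2), no blinding (Section 6.7) and no data monitoring committee (Section 11.8).

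This matters more here than in most extension studies. The population has a progressive CNS disease, and the drug is given into the CSF through an implanted device. Section 7.21.2.1 names device-related events as one of three classes of event associated with intrathecal rhHNS. A new neurological sign, an infection or a CSF leak may plausibly be put down to drug, device, procedure or disease, and no comparator exists to check the choice. A clinical study report that followed the sentence literally could base its headline on the drug-attributed subset while the stated endpoint is all adverse events.

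**Working it through.** The protocol gives no figure to reproduce on this point. Section 10.2 sets the sample size by roll-over from HGT-SAN-055, and Section 10.6.1.1 rules out formal tests on safety. The check is therefore a comparison of passages.

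**Which adverse events count, by place in the protocol**

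- Section 3.1, primary endpoint: adverse events "as measured by adverse events (by type and severity"; no attribution condition.
- Section 2.1, primary objective: long-term safety and tolerability in patients "who received rhHNS via a surgically implanted intrathecal drug delivery device (IDDD"; the device is part of what is being studied.
- Section 10.1: adverse experiences tabulated by dose group; no attribution condition.
- Section 10.6.1.1, opening sentence: treatment-emergent events attributed to study drug; described as the primary basis.
- Section 10.6.1.1, tables: any event, by system organ class and by individual event, from Study Day 1; relatedness is a breakdown.
- Section 10.6.1.1, device summary: events probably or possibly related to the device, by dose group and overall.

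Five of these six places are either all-causality or explicitly take in the device. The sixth, the opening sentence, is the only one that says what the assessment primarily rests on, and it carries the restriction. The section therefore gives two answers to the question of what the primary adverse-event measure is.

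**Where a non-drug event goes.** Take an IDDD infection judged device-related and not drug-related. It appears in the any-event table, in the system organ class table, in the serious-event listing if serious, in the device summary and in the full listings. It does not meet the condition in the opening sentence. It is reported, but it is not part of the stated primary adverse-event basis.

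**How strong the filter is.** Table 7-5 grades drug relatedness as not, possibly, probably or definitely related. The opening sentence does not say which grades qualify, so the strength of the filter is not fixed.

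**Scale.** Section 10.2 gives a maximum of 12 patients. If k patients have only events judged unrelated to drug, the all-causality and drug-attributed proportions differ by k/12. For k = 1 that is 1/12 = 8.3 percentage points; for k = 6 it is 6/12 = 50 points. The values of k are assumptions, since the protocol gives no event rates.

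**A related gap in the device summary.** It names only probably and possibly related events, while the scale in Table 7-5, which is written for study drug, also has a definite category. Read literally, the most clearly device-related events would be left out of the summary meant for them.

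**The case against.** The strongest reply is that the sentence is introductory and nothing operates on it. No table, threshold, test or stopping rule uses a drug-related-only rate. The rules that follow it base the summaries on all events from Study Day 1, and the vital-sign and laboratory half of the sentence has no attribution condition. This stands as far as data and tables go: nothing is lost from collection or reporting.

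It also disposes of a stronger reading that a reader might infer, namely that device and procedure harm is dropped from the analysis. The documents do not support that. Section 10.6.1.1 plans all-event tables, a serious-event listing and a device summary, and it lists all safety data.

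A reader might also infer from Table 7-5 that the filter removes nearly everything, because a probably related event is one that "follows a clinically reasonable response on de-challenge", which is hard to observe under continuing dosing. That goes too far as well. The possibly related grade needs no de-challenge, and it expressly admits events that concurrent disease could explain. A competing disease explanation therefore does not by itself make an event unrelated.

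The reply does not remove the contradiction. A descriptive trial with no tests draws its safety conclusion from whatever its plan calls primary, and here that is the drug-attributed subset. All-causality tables elsewhere in the section do not settle which measure the conclusion should use.

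**Conclusion.** The sentence is wrong as written. It contradicts the primary endpoint, the objective that includes the implanted device, and the tables in its own section. It also makes the adverse-event part of the primary basis depend on unblinded causality judgments with no comparator.

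The defect is confined to the stated basis of the safety conclusion; device, procedure and disease-attributed events remain in the planned outputs. Its numerical effect cannot be derived from the protocol. The k/12 figures show the mechanism and predict nothing.

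The conclusion rests on reading the qualifier literally. It also rests on the original protocol and Amendment 1, the only versions that could be read. The cover lists amendments up to Amendment 8, dated 01 February 2017, and the SAP was not available. Either could already have corrected the sentence.

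**What to change.** In Section 10.6.1.1, delete the last four words of the clause quoted above, which limit the events to those due to the drug. State instead that safety is assessed primarily on all treatment-emergent adverse events by type and severity, regardless of attribution, together with the vital-sign and laboratory component already named. Keep drug-related and device-related events as the breakdowns that the section already plans. Extend the device summary to definitely related events.

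The sponsor should first check whether the phrase is still present in the later amendments and in the SAP.

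The cost is small: a wording change and no new tables. One point of data collection needs checking. Section 7.21.3.2 requires a relationship to study medication for every event, while a judgment on the device is stated only for serious events in Section 7.21.3.1. If the case report form does not record device relatedness for non-serious events, the existing device summary already depends on a field that would have to be added. The other cost is that the headline safety statement may be less favourable, because it would count events that the present wording leaves to secondary tables.
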